8.2 Serious Adverse Events

An adverse event or adverse reaction is considered serious if, in the view of either the Investigator or Sponsor, it results in any of the following outcomes:

- Death
- A life-threatening adverse event
 - An adverse event or adverse reaction is considered “life-threatening” if, in view of either the Investigator or Sponsor, its occurrence places the patient at immediate risk of death. It does not include an event that, had it occurred in a more severe form, might have caused death
- Requires hospitalization or prolongation of existing hospitalizations
 - Any hospital admission with at least 1 overnight stay will be considered an inpatient hospitalization. An emergency room visit without hospital admission will not be recorded as an SAE under this criterion, nor will hospitalization for a procedure scheduled or planned before signing of informed consent. However, unexpected complications and/or prolongation of hospitalization that occur during elective surgery should be recorded as

adverse events and assessed for seriousness. Admission to the hospital for social or situational reasons (i.e., no place to stay, live too far away to come for hospital visits) will not be considered inpatient hospitalizations

- A persistent or significant disability/incapacity or substantial disruption of the ability to conduct normal life functions
- A congenital anomaly/birth defect
- An important medical event
 - Important medical events that may not result in death, be life-threatening, or require hospitalization may be considered an SAE when, based upon appropriate medical judgment, they may jeopardize the patient and may require medical or surgical intervention to prevent one of the outcomes listed above. Examples of such medical events include allergic bronchospasm requiring intensive treatment in an emergency room or at home, blood dyscrasias or convulsions that do not result in inpatient hospitalizations, or the development of drug dependency

8.3 Serious Adverse Event Reporting – Procedures for Investigators

Initial Reports

All SAEs occurring from the time of informed consent until 30 days following the last administration of study drug must be reported to [REDACTED] within 24 hours of the knowledge of the occurrence (this refers to any adverse event that meets any of the aforementioned serious criteria). All SAEs that the Investigator considers related to study drug occurring after the 30-day Follow-up Period must be reported to the Sponsor.

To report the SAE, the Investigator must complete the SAE form electronically in the electronic data capture (EDC) system for the study. When the form is completed, [REDACTED] personnel will be notified electronically and will retrieve the form. If the event meets seriousness criteria and it is not possible to access the EDC system, the Investigator should send an e-mail to [REDACTED] or call the Medpace Clinical Safety SAE reporting line (phone number listed below), and fax the completed paper SAE form to [REDACTED] (fax number listed below) within 24 hours of awareness. When the EDC system becomes available, the SAE information must be entered within 24 hours of the system becoming available.

Safety Contact Information: [REDACTED]

[REDACTED]

[REDACTED]

Follow-up Reports

The Investigator must continue to follow the patient until the SAE has subsided or until the condition becomes chronic in nature, stabilizes (in the case of persistent impairment), or the patient dies.

Within 24 hours of receipt of follow-up information, the Investigator must update the SAE form electronically in the EDC system for the study and submit any supporting documentation (e.g., patient discharge summary or autopsy reports) to [REDACTED] via fax or e-mail. If it is not possible to access the EDC system, refer to the procedures outlined above for initial reporting of SAEs.

8.4 Expedited Reporting

The Sponsor will comply with all country-specific regulations relating to safety reporting to the regulatory authority, Institutional Review Board (IRB)/Independent Ethics Committee (IEC), and Investigators.

The Sponsor will report all relevant information about suspected unexpected serious adverse reactions that are fatal or life-threatening as soon as possible to the Food and Drug Administration (FDA), applicable competent authorities in all the Member States concerned, and to the Central Ethics Committee, and in any case no later than 7 days after knowledge by the Sponsor of such a case, and that relevant follow-up information will subsequently be communicated within an additional 8 days.

All other suspected unexpected serious adverse reactions will be reported to the FDA, applicable competent authorities concerned, and to the Central Ethics Committee as soon as possible but within a maximum of 15 days of first knowledge by the Sponsor.

The Sponsor will also inform all Investigators as required.

Expedited reporting of suspected unexpected serious adverse reactions related to APX001 will not be necessary. Listings of cases related to APX001 will be included in the Development Safety Update Report.

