CLINICAL STUDY PROTOCOL

An Open-Label Study to Evaluate the Efficacy and Safety of APX001 in Non-Neutropenic Patients with Candidemia, with or without Invasive Candidiasis, Inclusive of Patients with Suspected Resistance to Standard of Care Antifungal Treatment

Investigational Product: APX001

Protocol Number: APX001-201

EudraCT Number: 2017-003571-56

Sponsor:

Amplyx Pharmaceuticals, Inc.
[name]
USA

[contact]

[contact]

Amendment Number: 2.0

Protocol Version Number: 3.0

Date: 03 June 2019

Confidentiality Statement

The information in this document is confidential and is not to be disclosed without the written consent of Amplyx Pharmaceuticals, Inc. except to the extent that disclosure would be required by law and for the purpose of evaluating and/or conducting a clinical study for Amplyx

Pharmaceuticals, Inc. You are allowed to disclose the contents of this document only to your Institutional Review Board and study personnel directly involved with conducting this protocol.

Persons to whom the information is disclosed must be informed that the information is confidential and proprietary to Amplyx Pharmaceuticals, Inc. and that it may not be further disclosed to third parties.

SYNOPSIS

TITLE: An Open-Label Study to Evaluate the Efficacy and Safety of APX001 in Non-Neutropenic Patients with Candidemia, with or without Invasive Candidiasis, Inclusive of Patients with Suspected Resistance to Standard of Care Antifungal Treatment

PROTOCOL NUMBER: APX001-201

INVESTIGATIONAL PRODUCT: APX001

PHASE: 2

INDICATION: Treatment of non-neutropenic patients with candidemia – inclusive of those patients with suspected or confirmed antifungal-resistant candidemia

OBJECTIVES:

The primary objective of this study is to evaluate the efficacy and safety of APX001 for the treatment of adult non-neutropenic patients ≥ 18 years of age with candidemia that may include patients with suspected or confirmed resistance to standard of care (SOC) antifungal treatment.

The secondary objectives of this study are to:

- Evaluate the time to first negative blood culture
 - Evaluate the percentage of patients with Mycological Outcomes at End of Study Drug Treatment (EOST), End of Antifungal Treatment (EOT), and 2 and 4 weeks after EOT
 - Evaluate the percentage of patients with Treatment Success at EOT, and 2 and 4 weeks after EOT
 - Evaluate overall survival at Study Day 30

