6.4.3 End of Study Drug Treatment

The EOST occurs after completion of APX001 dosing. The following procedures will be performed at EOST:

- Record vital signs, including temperature, blood pressure, heart rate, respiratory rate, oxygen saturation, and weight
- Intravascular catheter management log
- Perform dilated fundoscopic examination (only required in those patients who had positive fundoscopic findings at Screening, or as clinically indicated)
- Perform clinical laboratory assessments (serum chemistry, hematology, coagulation, and urinalysis)
- Perform 12-lead ECG
- Perform urine pregnancy test (for females of childbearing potential only)
- Perform focused, symptom-based physical examination including a neurological examination
- Collect blood culture for *Candida* spp. and blood for *Candida* spp. testing by T2MR assay
- Collect plasma sample for PK (APX001 [prodrug] and APX001A [active moiety])
 - Optional: If body fluids are sampled as part of routine patient management (e.g., bronchoalveolar lavage, lumbar puncture, paracentesis, vitreal fluid collection, abscess drainage), within approximately 2 hours of blood sampling for PK, these samples may be stored for future analysis of APX001 and APX001A levels.
- Collect other cultures and histopathology from other sites, as clinically indicated to monitor the site(s) and extent of candidemia infection
- Perform imaging tests as clinically indicated to monitor the site(s) and extent of candidemia infection
- Collect serum sample for analysis of (1,3)- β -D-glucan
- Evaluate treatment outcome
- Record concomitant medications
- Assess adverse events

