8.1.1 Adverse (Drug) Reaction

All noxious and unintended responses to a study drug related to any dose should be considered an adverse drug reaction. “Responses” to a study drug means that a causal relationship between a study drug and an adverse event is at least a reasonable possibility, i.e., the relationship cannot be ruled out.

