8.1.2 Unexpected Adverse Drug Reaction

An unexpected adverse drug reaction is defined as an adverse reaction, the nature or severity of which is not consistent with the applicable product information. For APX001, the reference safety information is included in the Investigator’s Brochure (IB) currently in force. The reference safety

information will be reviewed yearly and the periodicity of the review will be harmonized with the reporting period of the Development Safety Update Report.

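### Protocol Section 8.4 sets 7- and 15-day deadlines for every SUSAR, then says SUSARs related to APX001, the only study drug, need no expedited reporting

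*Protocol*

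**What the plan says.** Section 8.4 of the protocol opens with a general promise to follow each country's safety-reporting regulations. It then sets two deadlines for the sponsor.

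- Fatal or life-threatening SUSARs go to the FDA, the competent authorities of the Member States concerned and the Central Ethics Committee, "in any case no later than 7 days after knowledge by the Sponsor of such a case". Follow-up information is due within a further 8 days.
- For the rest, "All other suspected unexpected serious adverse reactions will be reported to the FDA, applicable competent authorities concerned" and the Central Ethics Committee within 15 days.

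Neither deadline is limited to a particular product. The section adds that investigators will also be informed as required.

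The last paragraph of the same section reads: "Expedited reporting of suspected unexpected serious adverse reactions related to APX001 will not be necessary". The next sentence gives the alternative route: "Listings of cases related to APX001 will be included in the Development Safety Update Report".

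The SAP does not address expedited reporting.

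**The concern.** The deadlines and the exemption appear to apply to the same events. A reader responsible for safety reporting would find two opposite instructions within one section on a core duty to regulators and ethics committees.

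The matter is not academic for this drug. According to Section 1, the completed clinical experience is two Phase 1 studies with 166 healthy volunteers enrolled and no serious adverse events reported. A serious reaction judged related to APX001 in a patient with candidemia could therefore well be unexpected. That is an inference, because the Investigator's Brochure is not among the documents. If the exemption were applied, regulators and ethics committees, and possibly investigators at other sites, might first learn of such a case from a periodic report, while roughly 20 sites continued to enroll and dose.

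**Working it through.** The protocol gives no figure to reproduce here. The check is whether the exempted cases are the same as the cases under the deadlines, followed by the size of the delay if the exemption were used.

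**Step 1: what the deadlines cover.** Fatal or life-threatening SUSARs (7 days) plus all other SUSARs (15 days) make up all SUSARs.

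**Step 2: what a SUSAR is in this protocol.**

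- Section 8.1.1 ties a reaction to the study drug: "All noxious and unintended responses to a study drug related to any dose should be considered an adverse drug reaction".
- The title page names one product: "Investigational Product: APX001". Section 3.1 describes a single-arm study without a comparator.
- Section 6.4.3 equates study drug treatment with APX001 treatment: "The EOST occurs after completion of APX001 dosing".
- Section 8.1.2 judges expectedness against reference safety information and names a source for APX001 only.

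A SUSAR under these definitions is therefore a SUSAR related to APX001.

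**Step 3: compare the two.** The deadlines cover all SUSARs. The exemption covers SUSARs related to APX001. By Step 2 these are essentially the same set, so the exemption leaves the deadlines with almost nothing to act on.

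**Step 4: test the other possible reading.** The deadlines might have been meant for step-down fluconazole (Sections 5.2.3 and 5.6.3) and the exemption for APX001. The text does not support this. The deadlines name no product, fluconazole is not called study drug or investigational product, and no reference safety information is given for it. Even on that reading, the 15-day rule applies to all remaining SUSARs and would still conflict with the exemption.

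**Step 5: size of the delay if the exemption is followed.** The documents do not state a DSUR interval. Section 8.1.2 says that the reference safety "information will be reviewed yearly and the periodicity of the review will be harmonized with the" DSUR reporting period, which implies a yearly cycle. Both rows below are assumptions, and time to prepare the report is left out.

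| Assumed DSUR cycle | Longest wait | Beyond the 7-day limit | Beyond the 15-day limit |
|---|---|---|---|
| 12 months | 365 days | 365 − 7 = 358 days | 365 − 15 = 350 days |
| 6 months | about 183 days | 183 − 7 = 176 days | 183 − 15 = 168 days |

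If cases fall evenly over a yearly cycle, the mean wait is 365 / 2, about 183 days. For scale, Section 3.1 puts one patient's participation at up to about 7.5 weeks, which is 7.5 × 7 = 52.5 days. A full yearly wait is 365 / 52.5 = 6.95 times as long, so later patients could enroll and finish before notice was given.

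**The case against.** The strongest counter-argument is that Section 8.4 already commits the sponsor to all country-specific safety-reporting rules, and that saying expedited reporting is not necessary does not forbid it. Section 11.5 also requires conduct in line with GCP, Directive 2001/20/EC and applicable regulations. A sponsor that keeps to these commitments would report on time wherever the law requires it. This stands as a reason to think the harm less likely. It does not remove the conflict, because the general commitment does not say which of the two specific instructions prevails, and Section 11.5 is addressed to the investigator.

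Second, other channels exist. Investigators report serious adverse events within 24 hours (Section 8.3), the DSMB can suspend enrollment at any time (Sections 8.5.1 and 9.2.5), investigators pass safety updates to their ethics committees (Section 11.2), and Section 8.4 says that investigators will be informed as required. These are genuine safeguards, and because of them a periodic report need not be the only way an ethics committee or another site hears of a case. None of them gives regulators expedited notice, and the safety updates in Section 11.2 carry no deadline.

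Third, the day counts rest on an assumed reporting cycle, the six-month case has no basis in the text, and no SUSAR rate is given. That is correct. The contradiction does not depend on them.

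Fourth, the documents do not say what the closing sentence was intended to exempt. That also stands, and it affects how the sponsor should carry out the correction.

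**Conclusion.** The concern holds. Section 8.4 gives two incompatible instructions for essentially every SUSAR that this trial can produce, and no other part of the protocol or SAP settles which applies. This conclusion needs only the protocol's own text.

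The size is conditional on the closing sentence being followed: notice at the next DSUR instead of within 7 or 15 days. That is up to 350 to 358 days late on an assumed yearly cycle and 168 to 176 days late on an assumed six-month cycle.

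No endpoint, analysis population or estimate is affected. The point must be fixed because it concerns patient safety and the clarity of a reporting duty.

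**What to change.** Delete the sentence that exempts SUSARs related to APX001, so that the 7- and 15-day deadlines in the same section apply to them without exception. Reword the final sentence to say that these cases will also be listed in the DSUR, in addition to expedited reporting. The rest of Section 8.4 supports this direction: the regulatory commitment, the two deadlines, the named recipients, the follow-up limit and the duty to inform investigators all point the same way.

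When making the change, the sponsor should confirm what the deleted sentence was meant to achieve and check that the safety management procedures do not repeat it.

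The cost is one sentence deleted and one reworded in a protocol amendment. No additional data, visits or analyses are needed, and the SAP does not change.

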8.5 Stopping Rules

8.5.1 Study Stopping Rule

At any time, the independent DSMB may temporarily suspend enrollment until any significant safety concerns are resolved or terminate the study to ensure patient safety, if in the opinion of the DSMB, further dosing would pose an inappropriate safety risk. Guidelines for what constitutes inappropriate safety risks are described in the DSMB Charter.

8.5.2 Subject Stopping Rule

Study treatment for an individual patient may be discontinued for lack of clinical and/or microbiological response, any adverse event, SAE, laboratory abnormality, or intercurrent illness which, in the opinion of the Investigator, indicates that continued dosing in the study is not in the best interest of the patient.

8.6 Pregnancy Reporting

A urine pregnancy test will be performed at Screening and Baseline (pre-dose), every 30 days during treatment if required by local regulations, EOST, EOT, and 2 and 4 weeks after EOT, or Early Termination for all female patients of childbearing potential. If the patient or partner of a patient participating in the study becomes pregnant during the study or within 30 days of discontinuing study drug, the Investigator should report the pregnancy to [REDACTED] within 24 hours of being notified. [REDACTED] will then forward the Exposure In Utero Form to the Investigator for completion.

A patient becoming pregnant while on study drug will immediately be withdrawn from the study and Early Termination study procedures will be performed.

The patient or partner should be followed by the Investigator until completion of the pregnancy. If the pregnancy ends for any reason before the anticipated date, the Investigator should notify [REDACTED]. At the completion of the pregnancy, the Investigator will document the outcome of the pregnancy within 24 hours. If the outcome of the pregnancy meets the criteria for immediate classification as an SAE (i.e., postpartum complication, spontaneous abortion, stillbirth, neonatal death, or congenital anomaly), the Investigator should follow the procedures for reporting an SAE.

8.7 Clinical Laboratory Evaluations

Screening laboratory assessments to determine eligibility will be performed at the local laboratory and may have been collected as SOC within the previous 24 hours. Laboratory assessments collected after Screening will be sent to the central laboratory for analysis.

Clinical laboratory assessments (serum chemistry, hematology, coagulation, and urinalysis) will occur at Screening, Baseline (pre-dose), twice weekly during Study Drug Treatment, at EOST, EOT, and 2 and 4 weeks after EOT, or Early Termination. If clinically indicated and at the discretion of the Investigator, or if a suspected adverse event is identified, clinical laboratory assessments may be conducted at any time during the study and compared to Baseline. See Appendix B for a complete list of clinical laboratory analytes.

8.8 Vital Signs

Vital signs will include temperature, blood pressure, heart rate, respiratory rate, oxygen saturation, and weight and will be collected at Screening, Baseline (pre-dose), daily on Study Days 2 through 4, and twice weekly thereafter during Study Drug Treatment, at EOST, EOT, and 2 and 4 weeks after EOT, or Early Termination. Height will be collected (from the patient's medical record) at Baseline.

8.9 APACHE II Score

The APACHE II score (Appendix C) will be determined at Baseline (pre-dose).

8.10 Electrocardiograms

A 12-lead ECG will be obtained at Baseline (pre-dose), EOST, EOT, and 4 weeks after EOT, or Early Termination.

8.11 Physical Examinations

A complete physical examination will be conducted at Baseline (pre-dose). Complete physical examination will include an assessment of general appearance, skin, eyes, heart, chest, abdomen, the body site that corresponds to the entry site of candidemia (e.g., central venous catheter entry site), if applicable, and a neurological examination. Components of the neurological examination include cranial nerve, sensory and motor examination, reflex and gait testing, and coordination assessment.

A focused, symptom-based physical examination to include a neurological examination will be performed once weekly during study treatment, EOST, EOT, and 2 and 4 weeks after EOT, or Early Termination.

8.12 Pharmacokinetics

Plasma samples for PK (APX001 [prodrug] and APX001A [active moiety]) will be collected at Baseline (pre-dose), twice weekly during Study Drug Treatment, EOST, EOT, and 2 weeks after EOT, or Early Termination.

Optionally, if body fluids are sampled as part of routine patient management (e.g., bronchoalveolar lavage, lumbar puncture, paracentesis, vitreal fluid collection, abscess drainage), within approximately 2 hours of blood sampling for PK, these samples may be stored for future analysis of APX001 and APX001A levels.

8.13 Dilated Fundoscopic Examination

A dilated fundoscopic examination will be performed at Screening for all patients and at EOST, EOT, and 4 weeks after EOT, or Early Termination for those patients who had positive fundoscopic findings at Screening, or as clinically indicated.

8.14 Imaging Tests

Imaging should be performed to assess the site(s) and extent of candidemia infection as clinically indicated.

8.15 Other Cultures and Histopathology

Other cultures and histopathology should be performed to assess the site(s) and extent of candidemia infection as clinically indicated.

8.16 Intravascular Catheter/Device Management Log

The management of intravascular catheters, intravascular devices, and, if applicable, any drains will be recorded, including any associated microbiology results.

9 STATISTICS

9.1 Analysis Populations

Intent-to-Treat Population/Safety Population

The Intent-to-Treat Population/Safety Population will include all patients who have received at least 1 dose of APX001.

Modified Intent-to-Treat Population

The Modified Intent-to-Treat (MITT) Population will include all patients who satisfy the following criteria:

- Received at least 1 dose of study drug
- Have a confirmed diagnosis of candidemia within 96 hours of the start of treatment with APX001

Per-Protocol Population

The Per-Protocol Population will include all patients who satisfy the following criteria:

- Received at least 1 dose of study drug
- Have a confirmed diagnosis of candidemia within 96 hours of the start of treatment with APX001
- Did not exceed prior antifungal treatment (per eligibility)
- Meet the protocol's key inclusion and exclusion criteria (to be defined in the study's Statistical Analysis Plan)
- Have no major protocol violations (to be defined in the study's Protocol Deviation Plan)

